As done in prior behavioral headache research,⁶⁹ all participants who attend at least ONE class will be included in the intention-to-treat analyses. This is a modified "intent to treat" analysis that ensures exposure to the independent variable and is used and felt to be very important by behavioral scientists.

Outcomes

Our primary outcome will be change in frequency of migraine days, defined as a calendar day (00:00 to 23:59)¹⁰² when the patient reports 4 or more continuous hours of a moderate to severe headache (rating of 6-10 on 0-10 VAS pain intensity scale) and/or they treated a headache with abortive medication. Participants will track their headaches daily with REDCap logs to

demonstrate frequency, severity (both pain intensity and pain unpleasantness, as trained with QST), medications, and associated migraine symptoms (e.g., photophobia, phonophobia, nausea, vomiting). iPod Touch devices with Pendragon software will be available to those without internet access.

Secondary outcomes include changes in migraine severity (measured by pain intensity and unpleasantness on 0-10 VAS scale), migraine duration (hrs), frequency of headache days, headache duration, headache severity (measured by pain intensity and unpleasantness on 0-10 VAS scale), experimental heat pain intensity and unpleasantness (QST measurements), and changes in scores on validated measures of mindfulness, pain acceptance, pain catastrophizing, emotional reactivity, and headache-related disability compared to an education control group; determine factors that predict MBSR response on migraine pain. A headache day is defined as any day when a participant reports the presence of a headache.

We will also characterize participants before/after the intervention using measures of hope, optimism, quality of life, depression, anxiety, perceived stress, self-efficacy, sleep, fatigue, pain interference, satisfaction with participation in social roles, allodynia, and global health.

All the secondary outcomes and additional measures will be assessed with these standardized, reliable, well-validated instruments: Five-Facet Mindfulness Questionnaire (mindfulness),^{57,103} DERS (emotion regulation),^{3,104} PCS (pain catastrophizing),^{2,36} Chronic Pain Acceptance Questionnaire (pain acceptance),¹⁰⁵ Herth Hope Index (hope),¹⁰⁶ Life Orientation Test-Revised (optimism),¹⁰⁷ Headache Impact Test-6 (HIT-6) (headache related disability),¹⁰⁸⁻¹¹⁰ Migraine Disability Assessment (MIDAS)-one month (headache related disability),^{111,112} Patient Health Questionnaire-depression module, PHQ-9 (depression),³⁴ Generalized Anxiety Disorder-7, GAD-7 (anxiety),³⁵ Headache Management Self-Efficacy Scale (self-efficacy),¹¹³ Migraine Specific Quality of Life Questionnaire, version 2.1 (MSQv2.1) (quality of life),^{114,115} the Perceived Stress Scale 10, PSS (perceived stress),¹¹⁶ the Brief Resilience Scale, the Resilience Scale for Adults, the Flourishing Scale, the Social Connectedness Scale-Revised (SCS-R), the Pittsburgh Sleep Quality Index, the Allodynia Symptom Checklist (ASC-12), and well-validated NIH Patient Reported Outcomes Measurement Information System (PROMIS) measures of sleep, fatigue, pain interference, satisfaction with participation in social roles, and global health. Changes from baseline to initial follow-up will be primary outcomes; secondary outcomes will include changes from baseline to follow-ups at 3 and 6 months.

Additional Information Collected

Sociodemographic and clinical information will be collected at the screening visit.

Expectations for improvement: Expectations can impact results.^{39,117} At baseline and after the second session, participants will rate their expectations using the Credibility/Expectancy Questionnaire.⁹⁶

Class Attendance and Home Practice: Participants in both groups will track their home activities up to the 6-month follow-up visit via REDCap logs and the instructors will track patient class attendance.

Qualitative Interviews: At the initial follow-up, a 30-minute semi-structured interview will be conducted with participants to further explore areas not captured in our standardized quantitative measures.

Data Analyses

Analysis 2a: The probability that an individual experiences a migraine on any given day will be examined as a function of group (MBSR vs. control) and treatment phase. A statistically significant group x phase interaction will be interpreted as evidence that treatment differentially

impacted the daily probability of migraine. This effect size will be indexed by converting the daily probability to headache counts as recommended for clinical trials in headache.¹¹⁸ If necessary we will model change using polynomial trajectories (i.e., growth curves) to better fit the time-course of treatment.

Analysis 2b: To examine this hypothesis, we will conduct an ANCOVA with pain unpleasantness at post-treatment as the dependent variable, group as the independent variable, and pain unpleasantness at pre-treatment as the covariate.

Analysis 2c: This analysis is identical to 2b, with the appropriate outcomes.

Analysis 3a: Baseline levels of pain catastrophizing and emotional reactivity will be used as predictors in the multilevel models predicting the trajectory of migraine attacks over the course of treatment.

Analyses 3b: This analysis is similar to 3a, except that changes in mindfulness (i.e., change scores from pre-treatment to post-treatment) will be used as predictor of migraine trajectory.

DATA COLLECTION AND QUALITY ASSURANCE

Data Collection Forms

Information will be collected from REDCap daily headache logs for appropriate diagnosis of migraines during an initial 4 week period prior to randomization and participants will continue to track daily headaches for the duration of the trial. Ipod touches with Pendragon software will be available to those without internet access and unable to use REDCap from home. Experimental heat measurements will be conducted at baseline and at each of the 3 follow-up evaluations. Participants will also complete standardized questionnaires using REDCap at baseline and at each of the 3 follow-up evaluations with an option to complete these questionnaires at home prior to the visit. In addition, a 30 minute qualitative interview will be conducted at the first follow-up visit to evaluate the participants' experience with the interventions. Each interview will be audiotaped. Socio-demographic and clinical information will also be collected at the screening visit.

Description of data that will be recorded on human subjects. Each 30 minute qualitative interview of the migraine and control subjects will be audiotaped and then transcribed. Participants will be photographed one of the study visits. These photos will be stored on the study's secure Ishare. Each subject will have provided informed consent to perform this.

Description of linkages to subjects and who will have access to subject identities. WFSM investigators and study staff will take measures to ensure the privacy and confidentiality of all study subjects. All participants will be assigned a study ID (unique ID) that will be used to link participant records and identify participants within the database. Only study investigators and the study team members will have access to the identity of participants.

Information about how specimens, records and data are collected; data collected specifically for research. All data are collected according to IRB approved study protocols specifically for research purposes. Specimens, records and data will be collected by study investigators, staff and physicians upon enrollment of the patients.

Quality Assurance

Protection Against Risk

Description of procedures for protecting against or minimizing potential risks, including risks to confidentiality, and assessment of likely effectiveness. All data collected will be completely confidential. Only investigators and their staff directly involved in this study will have access to the data. Records and forms will be kept in a locked file cabinet when not in use. No names will be stored on computer files for data analysis; no individuals will be identified in the results of this study. Access to computer-stored information will require knowledge of the data format, filename and password. [name] will use the results of this study for research only and

not include the results in a medical record. Any data that may be published in scientific journals will not reveal the subject's identity.

Plans for ensuring necessary medical or professional intervention in the event of adverse effects to the subjects. [name] is a trained clinician and will oversee the interventions. If a medical emergency arises the appropriate steps will be taken to contact emergency services.

Institutional Review Board (IRB) Review

This protocol and the informed consent document have been approved by Wake Forest's IRB (Wake Forest IRB protocol # IRB00027845).

PUBLICATION OF RESEARCH FINDINGS

We plan to publish our findings in top-tier scientific, peer-reviewed journals.

REFERENCES

1. Starr CJ, [name] TT, [name] RC. Psychological and sensory predictors of experimental thermal pain: a multifactorial model. *The journal of pain : official journal of the American Pain Society*. Dec 2010;11(12):1394-1402.

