Hypotheses: Migraineurs will report higher pain intensity and pain unpleasantness levels in response to experimentally induced pain than controls; (1b): Pain catastrophizing and emotional reactivity will moderate the association between pain unpleasantness and pain intensity; (1c): Pain catastrophizing and emotional reactivity scores will be positively associated with pain unpleasantness levels.

BACKGROUND AND RATIONALE

Background on Condition, Disease, or Other Primary Study Focus

Migraine is common and disabling. Migraine affects 36 million Americans and costs \$15 billion/year due to lost workdays, diminished productivity, and increased health care utilization.⁴⁻⁶ Affective/cognitive processes such as pain catastrophizing and emotional reactivity often play a major role in migraine pain and disability and may be just as important to target as the sensory aspect. High pain catastrophizing, a maladaptive cognitive process of exaggerated pain rumination,⁷⁻¹¹ is associated with more pain and disability across clinical pain syndromes, including headache.¹²⁻²¹ Affective disturbance is highly comorbid with migraine and associated with migraines becoming chronic.²²⁻²⁵ Due to this cognitive/affective load that builds over time in migraine, we hypothesize that migraine alters the relationship between the sensory and affective dimensions of pain processing.

Study Rationale

[figure not shown]

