We will conduct a cross-sectional study in migraineurs (interictally, i.e., between migraine attacks) and healthy controls to compare responses to experimental heat pain intensity and unpleasantness and correlate these results to differences in emotional reactivity and pain catastrophizing.

SELECTION AND ENROLLMENT OF PARTICIPANTS

Inclusion Criteria

Inclusion criteria for Healthy Controls: ≥18yo; pain free and healthy, without any major medical or psychiatric conditions

Inclusion Criteria for Migraineurs: ≥18yo with >1 yr of migraines and currently 4-20 days/month with migraines, although no migraine the day of study visit (see Table 1 for migraine diagnosis) or pain relieving medications within 12 hours of study visit.

Exclusion Criteria

Exclusion criteria for Healthy Controls: Diagnosis of migraine, probable migraine, Current regular (weekly or more often) practice of meditation or other mind-body intervention or frequent headaches of any type other than tension-type headaches on three or fewer days/month.

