Exclusion criteria for both: Any major unstable medical/psychiatric illness (e.g., hospitalization within 90 days, suicide risk, etc.); severe clinical depression/anxiety (with PHQ-9 scores >20); chronic pain condition (e.g., fibromyalgia, migraines for healthy controls, etc.) or sensory abnormalities (e.g., neuropathy, Raynaud's, etc.); current regular (weekly or more often) practice of meditation or other mind-body intervention; diagnosis of medication overuse headache or chronic migraine. Migraineurs will be studied if they have been headache-free the day of the study visit. Participants may be currently taking migraine medications, as long as they do not have a diagnosis of medication overuse headache. Volunteers with no pain ratings to frankly noxious stimuli (temperatures > 49°C) or excessive responses to threshold temperatures (~43°C) will be excluded. Pregnant subjects will be excluded from all portions of the study due to possible unknown risks of frankly noxious stimuli. Due to unknown risks and potential harm to the unborn fetus, sexually active women of childbearing potential must use a reliable method of birth control while participating in this study. Reliable methods of birth control are: abstinence (not having sex), oral contraceptives, intrauterine device (IUD), DepoProvera, tubal ligation, or vasectomy of the partner (with confirmed negative sperm counts) in a monogamous relationship (same partner). An acceptable, although less reliable, method involves the careful use of condoms and spermicidal foam or gel and/or a cervical cap or sponge.

Table 1: Migraine Diagnosis*

- | |
|--|
| 
• At least 5 attacks, not attributable to another disorder, with:
• Headache lasting 4-72 hours (untreated or unsuccessfully treated)• Headache with at least 2 of the 4:
• Unilateral location• Pulsating quality• Moderate or severe pain intensity• Aggravation by or causing avoidance of routine physical activity (e.g. walking or climbing stairs)• During headache at least 1 of the 2:
• Nausea and/or vomiting• Photophobia and phonophobia |
|--|

*According to the International Classification of Headache Disorders-II Guidelines

Study Enrollment Procedures

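### Part 1 states an analgesic-free test-day condition for migraineurs only and screens only controls for stable psychiatric illness, so part of any group difference may reflect who was tested and under what conditions

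*Combined protocol and SAP*

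**What the plan says.** All of this is in the combined protocol and SAP, Part 1.

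- **Inclusion Criteria, controls:** "Inclusion criteria for Healthy Controls: ≥18yo; pain free and healthy, without any major medical or psychiatric conditions". This bars stable as well as unstable psychiatric illness.
- **Exclusion criteria for both groups:** "Any major unstable medical/psychiatric illness (e.g., hospitalization within 90 days, suicide risk, etc".) and "severe clinical depression/anxiety (with PHQ-9 scores >20"). These are the only psychiatric limits on migraineurs.
- **Inclusion Criteria, migraineurs:** no migraine on the day of the visit, "or pain relieving medications within 12 hours of study visit".
- **Exclusion criteria, controls:** the list opens "Exclusion criteria for Healthy Controls: Diagnosis of migraine, probable migraine, Current regular (weekly or more often) practice of meditation or other mind-body intervention" and goes on to bar "frequent headaches of any type other than tension-type headaches on three or fewer days/month". It contains no medication item.
- **Required Interventions** reschedules a participant who arrives with a headache. **Prohibited Interventions** is marked not applicable.
- **Study Enrollment Procedures** matches on age, gender and race.
- **Data Analyses:** model 1a contains group, stimulus and block. Model 1b adds pain intensity.
- **Tables 6 and 7** (the Part 1 schedules for migraineurs and healthy volunteers) both list PHQ-9 and GAD-7.

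**The concern.** The Study Rationale hopes that heat-pain testing can become a marker of migraine activity. That reading needs a group difference that can be attributed to migraine. Two other determinants of the ratings are handled differently in the two groups, and neither matching nor the models address them.

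The first is the test-day condition. By imposing an analgesic-free window on migraineurs, the plan implies that recent analgesics matter to the ratings, yet it standardises only one group. A control who took an analgesic for a permitted tension-type headache, and is headache-free on arrival, passes every stated check.

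The second is psychiatric selection. The Background says "Affective disturbance is highly comorbid with migraine", so affect lies close to what is being studied. A control with a major but stable condition is turned away, while a migraineur with the same condition is enrolled. The measures most exposed are unpleasantness (1a and 1b) and the Pain Catastrophizing Scale (PCS) and Difficulty in Emotion Regulation Scale (DERS) scores. The primary objective names catastrophizing and emotional reactivity in the migraineur-versus-control contrast.

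**Working it through.** **Step 1. Does any other Part 1 text close either gap?**

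| Item | Migraineurs | Controls | Closed elsewhere? |
|---|---|---|---|
| Analgesic-free window | 12 hours | None stated | No. Required Interventions covers only a headache present on arrival. The other mention is the Part 2 screening visit, which has no controls. |
| Major stable psychiatric illness | Eligible | Excluded | No. The joint exclusions cover only unstable illness and PHQ-9 above 20. |
| Model term in 1a or 1b | None | None | Intensity in 1b should absorb an analgesic effect that lowers both ratings. It does not remove a difference in affect, because 1b tests the part of unpleasantness left after intensity. |

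Both asymmetries stand.

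**Step 2. The plan's yardstick.** Sample Size and Randomization gives a control mean of 3, SD 2, a detectable migraineur mean of 4.24, d = 0.62 and 48 per group. The difference is 4.24 − 3 = 1.24, and 1.24 / 2 = 0.62, so the example is consistent with itself. The power statement does not reproduce exactly. At two-sided 0.05 (Part 1 states no alpha), a single measurement with 48 per group gives 85.9% power at d = 0.62, against the stated 80%. The stated figure is therefore conservative and does not affect this point. The 1.24 serves below only as a scale.

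**Step 3. Analgesic effect.** Bias = (share of controls tested soon after an analgesic) × (drop in rating). Both inputs are assumptions.

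- Low: 0.02 × 0.5 = 0.01 points; 0.01 / 1.24 = 0.8%.
- High: 0.10 × 1.5 = 0.15 points; 0.15 / 1.24 = 12%.

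The 10% share is about the ceiling if tension-type headache is the route and visits fall at random: 3 days of about 30 is 10%, with every control at the limit and treating every headache. If use for other reasons took it to 20%, the high end would be 0.20 × 1.5 = 0.30 points.

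Effect of 0.15 points on the false-positive rate if there were no true difference, at two-sided 0.05:

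- One measurement: SE = 2 × √(2/48) = 0.408; 0.15 / 0.408 = 0.37; rejection rate 6.6%.
- Twelve ratings (4 temperatures × 3) with the plan's correlation of 0.5: variance factor (1 + 11 × 0.5) / 12 = 0.542; SE = 0.408 × √0.542 = 0.300; 0.15 / 0.300 = 0.50; rejection rate 7.9%.

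**Step 4. Psychiatric selection.** The clause can change only the control mean. Its contribution is (share of otherwise eligible controls whom it removes) × (shift in rating due to stable illness). Prevalence among migraineurs does not enter. The documents give neither input, so the calculation is shown for each 10 percentage points of controls removed:

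- 0.10 × 0.5 = 0.05 points (4% of 1.24)
- 0.10 × 1.0 = 0.10 points (8%)
- 0.10 × 1.5 = 0.15 points (12%)

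These figures show the scaling and are not an estimate.

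**Step 5. Direction.** Each asymmetry alone can lower control ratings. Two other provisions can work the other way. Migraineurs may continue their current treatments (Allowed Interventions), which may lower their ratings. Volunteers who respond excessively at about 43°C are excluded in both groups. If migraineurs are more heat-sensitive, as the Study Rationale states, that rule trims them more and narrows the contrast. No figure in the documents allows these to be netted.

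**The case against.** The strongest reply is that healthy controls are the declared comparator. The Study Rationale uses them as the reference towards which treatment might move migraineurs, and it treats affective load that builds up over time as part of the migraine mechanism. Comparing migraineurs as they present with psychiatrically healthy people is a legitimate descriptive contrast, and adjusting for distress may remove part of the effect of interest. This stands. It is why the control definition should stay and the adjusted model should be secondary. It does not remove the need to say what the primary contrast means.

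On analgesics, controls must be free of pain and an active headache leads to rescheduling, so recent use is probably uncommon. This also stands: the effect is likely small. But the text does not forbid such use.

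On PCS and DERS, Data Analyses specifies no group comparison, and analysis 1c uses them as predictors without a group term. This is only partly an answer, because the primary objective places those constructs in the group contrast.

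A reader might go further and infer that the psychiatric clause inflates the contrast by the prevalence of illness among migraineurs times its effect. The documents do not support that. If 30% of migraineurs and 10% of unscreened controls were affected, with a 1.0-point shift (all assumed), the clause would account for 0.10 × 1.0 = 0.10 points, not 0.30 × 1.0 = 0.30. The other 0.20 is excess illness in migraineurs, which would remain under identical criteria. A reader might also infer that the control clause is wrong and should be replaced. That is a choice of comparator on which statisticians can reasonably differ, and migraineurs recruited mainly from neurology clinics would still differ from community controls.

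**Conclusion.** The point holds in limited form. Two eligibility differences besides migraine are in the text, and nothing in the criteria, matching or models for 1a and 1b addresses them.

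The test-day analgesic gap probably has a small effect: 0.01 to 0.15 VAS points if 2 to 10% of controls are affected by 0.5 to 1.5 points. It is easily closed. The psychiatric difference means that some of any gap in unpleasantness, PCS or DERS may reflect how controls were selected. Its size is unknown and depends on the stable illness that the clause removes from controls.

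A conclusion that the two differences together inflate the migraine contrast would go too far. The documents contain no rates, and continued treatment and the exclusion of excessive responders may act in the opposite direction. Part 1 is not invalidated. What needs care is attributing the whole group difference to migraine.

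**What to change.** 1. Reconcile the migraineur and control criteria so that the same test-day analgesic condition, whichever the sponsor adopts, applies to both groups and is checked at the same visit step. Record recent analgesic use in both groups.
2. Keep the healthy-control definition. State in the Part 1 objectives and analysis section that the primary contrast is between migraineurs and psychiatrically screened healthy controls.
3. Prespecify, as a labelled sensitivity analysis, models 1a and 1b with PHQ-9 and GAD-7 added. Report both scores by group beside it: if screened controls cluster at low scores, overlap will be limited and the adjusted group effect will lean on the model.

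The cost is an eligibility edit, one screening question for controls, an occasional rescheduled control and one secondary analysis on data already scheduled. The adjusted model may over-adjust if migraine itself causes distress, so it should not replace the primary analysis. Where controls have already been tested, item 3 and the wording in item 2 need no new data.
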